## Study Summary

[figure not shown]
Title	Reducing Arrhythmia in Dialysis by Adjusting the Rx Electrolytes/Ultrafiltration
Short Title	RADAR
Protocol Number	
Phase	Pilot
Methodology	
Randomized, Crossover, Blinded, Multi-arm
 
Interventions:
 
Implanted Loop Recorder
 
Potassium/Bicarbonate Trial (Study A)
 
Ultrafiltration Trial (Study B)

Study Duration	24 months
Study Center(s)	
Duke University Medical Center (DUMC)
 
New York University Langone Health (NYU)-coordinating site receiving funding from the NIH with dialysis unit located at Lower Manhattan Dialysis Center ([name]).

Objectives	
 
• To obtain pilot data on adherence, safety and barriers to implementation of proposed interventions.
 
• To obtain pilot data on recruitment feasibility and subject retention.
 
• To obtain pilot data to estimate the potential effect sizes of proposed interventions.
 

Number of Participants	
40 (20 in each of two interventions)
 
(60 participants enrolled with 40 expected to reach randomization. Because patients have the option of enrolling in both study A and B it is possible that the total number of devices required will be less than 40.)

Diagnosis and Main Inclusion Criteria	Dialysis-dependent end-stage renal disease
Study Product/Intervention, Route, Regimen	
Study A: Potassium/Bicarbonate Four-Arm Crossover
 
Potassium (K) Removal Maximization strategy, 1 month (lower dialysate K)
 
Potassium (K) Gradient-Minimization Strategy, 1 month (higher dialysate K)
 
Acidosis Avoidance, 1 month (higher dialysate bicarbonate)
 
Alkalosis Avoidance, 1 month (lower dialysate bicarbonate)
 
Study B: Dialysis Ultrafiltration Rate (UFR) Two-Arm Crossover
 
UFR <math>\leq</math>10 ml/kg/hr, 1 month
 
UFR as needed, 1 month

Ancillary Products:	
LINQ™ (Medtronic) Implantable Cardiac Loop Recorder (Carelink System)
 
i-STAT (Abbott)- Study A only

Duration of administration	LINQ™: 3-6 months Study A: 4 months Study B: 2 months

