## II. Specific Aims

Overview of Trial Design—The overall goal for these trials is to provide the data necessary for the design of definitive clinical trials. Specifically, we aim to test recruitment feasibility, the feasibility of POC electrolyte measurement and POC-directed management of the dialysis prescription, and to provide preliminary estimates of effect size with manipulation of UF rate, dialysate K, and dialysate HCO3. We will perform two related, randomized cross-over trials; Study A- dialysate interventions trial, consisting of 2 dialysate potassium interventions and 2 dialysate bicarbonate interventions (4 total cross-over interventions); and Study B-ultrafiltration rate intervention trial, consisting of 2 separate ultrafiltration rate strategies.

The central hypothesis underlying Study A and Study B is that the risk of clinically significant arrhythmias in HD patients can be reduced by altering components of the dialysis prescription.

**Aim 1—To test the feasibility and safety of POC-guided dialysate prescription adjustment and the feasibility of limiting UF rate in HD patients.** The current studies will pilot our educational strategies and the dialysate potassium, dialysate bicarbonate and UF intervention strategies to test their feasibility in a multi-center setting. They will test the hypothesis that  $\geq 80\%$  adherence with proposed interventions is feasible, and that the safety need for unscheduled dialysis or severe abnormalities in potassium and bicarbonate will be minimal.

**Aim 2—To assess recruitment feasibility and retention rate for trials combining ILR insertion to monitor arrhythmia and interventions using POC-guided dialysis prescription or UF rate manipulation.** Screen failures and retention rates will be captured and analyzed. Whether recruitment rates  $\geq 1$  patient per month and retention rate  $> 90\%$  are achievable in each study will be tested.

**Aim 3—To refine effect estimates of the change in monthly CSA duration during Study A (dialysate potassium intervention to maximize vs. minimize intradialytic potassium removal) and Study B (aggressive vs. conservative ultrafiltration rate).** Refining estimates of change in CSA with each pair of interventions will provide key information necessary for design of definitive trials. Whether CSA decreases with minimization of potassium removal, alkalosis limitation and UF rate minimization will be tested.

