## **V. Description of Study Procedures**

Two related, randomized cross-over trials will be performed; Study A-a dialysate interventions trial, consisting of 2 dialysate potassium interventions and 2 dialysate bicarbonate interventions (4 total cross-over interventions); and Study B- an ultrafiltration rate intervention trial, consisting of 2 separate ultrafiltration rate strategies. A total of 20 patients will be enrolled in each trial. An overview of the study design is illustrated in **Figure 5 below**.

**ILR Intervention**— Consent and ILR placement at the local site will be followed by a one-month baseline observation period. ILR placement will be followed by wound check visits at 1 week and 1-month post implant. Outpatient insertion of ILR by study cardiologists will occur within 4 weeks of enrollment. Reveal LINQ™ (Medtronic) implantable monitors will be utilized.

**Arrhythmia Detection**—Detection of clinically significant arrhythmias (CSA) will be achieved using implantable loop monitors (ILR) inserted at the start of each trial. ILR tracings will be batch analyzed by study cardiologists blinded to randomized treatment. Tracings from ILR-detected events meeting automated, validated detection criteria for bradycardia, asystole, AF, sustained or non-sustained ventricular tachycardia (VT) will be manually reviewed at least once every two weeks. Clinically significant arrhythmias will be defined on the basis of arrhythmias likely to lead to sudden cardiac arrest or serious morbidity and mortality and will include atrial fibrillation (AF), asystole lasting  $\geq 3$  seconds, bradycardia  $\leq 40$  beats per minute lasting  $\geq 6$  seconds, sustained VT  $\geq 130$  beats per minute lasting  $\geq 30$  seconds, and any sudden cardiac arrest. Positively adjudicated CSA will be entered into a study database and coded according to arrhythmia type, date and duration.

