After ILR placement, subjects will crossover between two UF rate interventions: 1) UF rate-restricted dialysis, in which UF rates are limited to a maximum of 10 mL/kg/hr for the duration of the session 2) UF rate-unrestricted dialysis. It is anticipated that patients with large interdialytic weight gains in the UF rate-restricted intervention may not achieve their target post-dialysis weight during the prescribed treatment time. In order to prevent progressive volume overload and the need for additional HD sessions to manage volume gains in this scenario, subjects will crossover weekly between the restricted

and unrestricted UF interventions. This weekly crossover accomplishes two important goals: First, it reduces safety concerns by ensure that any volume gained due to limiting the UF are constrained to one week and promptly addressed with unlimited UF the following week. Second, it increases separation between UF rates in the two interventions, since a higher UF-rate will be needed to address any weight and volume gains resulting from UF-rate restriction.

Investigators will be blinded. Subjects will not be blinded as it is not feasible to blind them to the goal UF and post-dialysis weight (typically self-measured); HD staff will have access to the algorithm in order to adjust UF rate accordingly. Following a one-month baseline observation period with usual care, subjects will undergo 4 weeks of each UF intervention administered in alternating weeks as described above, for a total study duration of 12 weeks. Data will be aggregated and results compared using a full month of data for each intervention.

**End of Study Procedures**—In order to maximize recruitment efficiency and the significant investment in undergoing ILR implantation, patients completing one study will be given the option of continuing to eligibility screening and enrollment for the alternate study. If subjects consent to both Study A and Study B, then the baseline observation period for the second study may be less than 1 month. Those refusing or ineligible will be offered ILR explanation.

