**Study Visit #9: End of Treatment Visit**

Upon completion of either Study A or Study B, subjects will be screened and offered the opportunity to consent to participate in the other study. Subjects will be queried for adverse events and dialysis treatment records will be reviewed. If subjects elect to participate in both studies consecutively, then they will not need to redo the Week 1 Reveal insertion follow-up visits, since they will have already received a device. For subjects enrolling in both studies, a 1-week washout period is required (receive SOC hemodialysis treatment) and will then begin another 1-month of baseline monitoring prior to starting the intervention for the second study.

Once a subject has completed Study A and Study B, or a subject is no longer interested or eligible to participate in the second study, he or she will be given the option to come back to New York University Langone Medical Center for device removal. Subjects who choose to keep the device implanted after the last treatment will be followed for adverse events and concomitant medications for one week after this visit. Subjects who choose to have the device removed, will have two more study visits, one to remove the device and another to follow up on the removal procedure.

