**Safety Endpoints**—The primary safety endpoint will include the incidence of all serious adverse events and intervention-specific complications: a) Potassium Intervention—severe K abnormalities ( $K \geq 6.5$  or  $\leq 3.0$  mEq/L), or unscheduled HD or hospitalization for hyper/hypokalemia in the absence of a missed treatment; b) Bicarbonate Intervention—severe  $HCO_3$  abnormalities ( $HCO_3 < 20$  or  $> 32$  mEq/L) or unscheduled HD or hospitalization for acid base abnormalities in the absence of a missed treatment; c) Ultrafiltration Intervention—Unscheduled HD or hospitalization for volume overload. Secondary safety endpoints include the occurrence of CSAs requiring further management, all-cause mortality, cardiovascular mortality, and hospitalization.

**Recruitment Feasibility (Aim 2)**—Recruitment feasibility will be analyzed by testing whether an overall recruitment rate of 1 patient/month is achieved in each trial (1-sample test). This is a critical metric, as a large-scale trial cannot be feasibly completed in a practical number of centers if between 0.5-1 patient/month cannot be enrolled. This rate represents a minimum criterion for feasibility.

The percent of screened patients enrolled will be calculated as a secondary feasibility measure to assess the size of the necessary screening pool. Reasons for non-enrollment (vis-a-vis inclusion and exclusion criteria and patient and physician preferences) will be assessed to determine the potential for protocol modification to improve recruitment. Subject retention will be calculated as the percentage of enrolled patients completing the trial. Retention rates of 90% will be considered the benchmark for feasibility.

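### Patients who cross from one study to the other count towards the second trial's recruitment, screening yield and retention without facing the loop-recorder implant that Aim 2 is meant to test

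*Combined protocol and SAP*

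**What the plan says.** Aim 2 (section II) is "To assess recruitment feasibility and retention rate for trials combining ILR insertion to monitor arrhythmia" together with the dialysis interventions. The implant is therefore part of the trial whose feasibility is in question.

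Section V, End of Study Procedures, gives the reason for rollover: "In order to maximize recruitment efficiency and the significant investment in undergoing ILR implantation". It then provides that "patients completing one study will be given the option of continuing to eligibility screening and enrollment for the alternate study". The text for Study Visit #9 adds that patients doing both studies are screened and consented for the second, and that "they will not need to redo the Week 1 Reveal insertion follow-up visits, since they will have already received a device".

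Section V also states: "A total of 20 patients will be enrolled in each trial". The Study Summary gives "60 participants enrolled with 40 expected to reach randomization" and remarks that, because patients may join both studies, "it is possible that the total number of devices required will be less than 40".

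Section VI, Recruitment Feasibility (Aim 2), sets three measures:
- recruitment, tested against 1 patient/month in each trial;
- screening yield: "The percent of screened patients enrolled will be calculated as a secondary feasibility measure";
- retention, taken as completers over enrolled patients, with a 90% benchmark.

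None of the three is restricted to, or split by, patients new to the device. The overlap between the studies is acknowledged only in the device count.

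**The concern.** A patient who enters the second trial with a recorder in place has already passed the implant step, which is specific to this kind of trial. The patient must be screened and must consent again, but does not decide again about implantation. Read as written, section VI counts that patient as one recruit, one successful screen and one member of the retention denominator, exactly like a newly implanted patient.

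The protocol treats the recruitment rate as a minimum condition for a large trial, and feasibility data are this pilot's main product. If the 1 patient/month criterion is met partly by rollovers, a pooled figure will not show it, and planners may take it as evidence that patients accept implantation at that rate.

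**Working it through.** **1. Do rollovers fill places in the second trial?** Yes, by implication. There are 20 + 20 = 40 trial places. Fewer than 40 devices can serve 40 places only if some people fill two.

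**2. The plan's own figure.** The documents give no derivation of the recruitment or retention targets and no expected number of rollovers, so there is nothing to reproduce beyond 40/60 = 66.7% of enrolled patients reaching randomisation.

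**3. Recruitment.** Let f be the share of a trial's recruits who are rollovers (assumed). Then

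newly implanted rate = observed rate × (1 − f).

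At an observed 1.0/month (20 patients over an assumed 20 months):

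| Rollovers among 20 | f | Newly implanted per month |
|---|---|---|
| 0 | 0% | 1.00 |
| 5 | 25% | 15/20 = 0.75 |
| 10 | 50% | 10/20 = 0.50 |

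The accrual window is not stated. With 10 rollovers among 20 over an assumed 12, 18 or 24 months, the all-enrolled rate is 1.67, 1.11 or 0.83, and the newly implanted rate is 0.83, 0.56 or 0.42.

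**4. Why this is a lower bound.** Both trials screen the same affiliated units. Suppose a share d of the rollovers would have joined the second trial as new implants had the first not existed. A stand-alone trial would then see (1 − f) + d·f at an observed 1.0/month. With f = 50%, d = 0 gives 0.50 and d = 1 gives 1.00. The documents do not give d.

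**5. Effect on passing the benchmark.** Assume new patients arrive as a Poisson process at 0.6/month over 18 months (mean 0.6 × 18 = 10.8), and R rollovers are added. The chance of reaching 18 patients is P(N ≥ 18 − R): 3% for R = 0, 29% for R = 5 and 84% for R = 10. This allows no displacement of new recruits by the other trial, so it shows the mechanism at its strongest.

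**6. Retention among randomised patients.** Take 10 rollovers among 20, with assumed completion rates.
- New 80%, rollover 95%: (10 × 0.80 + 10 × 0.95)/20 = 87.5%, above the new-patient 80%.
- New 95%, rollover 80% (fatigue): (10 × 0.95 + 10 × 0.80)/20 = 87.5%, below the new-patient 95%.

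The same pooled figure can flatter or penalise the trial.

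**7. Retention on the enrolled denominator that section VI specifies.** Suppose new patients are lost before randomisation at the 60-to-40 rate, all rollovers are randomised, and 95% of everyone randomised completes. Retention is then 20 × 0.95/[R + 1.5(20 − R)]: 63% for R = 0, 69% for R = 5, 76% for R = 10 and 84% for R = 15. Under these assumptions rollovers raise the figure, but it stays below 90% throughout.

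**The case against.** Rollover is a deliberate and legitimate efficiency, and a later programme could keep it. The documents speak of definitive, subsequent multi-centre trials and never say that these will lack a pool of already-implanted patients. Rollovers also accepted implantation once under this same protocol, so dropping them discards real recruits whom a single trial might have enrolled directly. That stands, and it is why the device-naive rate must be labelled a lower bound and shown beside the all-enrolled rate.

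The number of rollovers is also limited. Study B requires a UF rate of at least 13 mL/kg/hour in at least 6 sessions in the prior month. Study A has haemoglobin and potassium exclusions. The first study must be finished, and everything fits within 24 months. This bounds the size but does not remove the mechanism.

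It may be said that prior participation will be known for every subject, so the split can be made at any time, and that the analyses are exploratory. True, but the recruitment rate is tested against a stated criterion, and its denominator is better fixed before the results are seen.

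Three stronger readings are tempting and are not supported:
- A reader might infer that (1 − f) is the rate a stand-alone trial would achieve. Step 4 shows that it is only the lower bound.
- A reader might infer that retention is also biased upwards. Rollovers are selected for having completed a study, but they repeat washout, baseline and a full intervention course. No document gives their completion rate.
- A reader might take 0.5/month as the plan's floor. Section VI tests 1/month and mentions 0.5–1 as a range.

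**Conclusion.** The concern holds for recruitment. As section VI is written, rollovers count in the second trial's recruitment rate, screening yield and retention without facing the implant step, and this can move the 1 patient/month result towards success. The recruitment effect is arithmetic once the rollover share is known, but that share is not given and the effect is zero if nobody rolls over. The 25% and 50% cases (0.75 and 0.50 newly implanted patients/month at an observed 1.0) are illustrations, not forecasts. For retention, an effect is plausible and its direction is open. Rollover itself is not a fault in the design; the gap is the missing split in the Aim 2 measures.

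**What to change.** In section VI, Recruitment Feasibility (Aim 2):
- Pre-specify the recruitment rate (tested against 1/month), screening yield and retention for first-time enrolees without a study recorder, in each trial.
- Show the all-enrolled figures alongside.
- Report rollovers on a separate line: number offered, consented and completed.
- State that the device-naive rate is a conservative, lower-bound estimate, and that the all-enrolled rate is not evidence of willingness to be implanted.
- Keep rollovers in the adherence, safety and arrhythmia analyses.

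This takes a few sentences and needs no extra patients, visits or data. The downside is that the feasibility figures rest on fewer subjects and may be less favourable.

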**Description of Study Visits:**

Subjects will meet with a member of the study team for 8-11 study visits, during regular dialysis treatments at their outpatient clinics. Study activities for each of the study visits are described below. In addition to the study visits, subjects will continue their regularly scheduled dialysis treatments and must receive at least half of the treatments at their outpatient clinic (6 out of 12 scheduled) for each treatment period and the 30-day Baseline Observation Period. \*Procedures for missed treatments for each period are described below. Adverse events will be collected from the date of consent until study visit #11. For subjects who elect to keep the ILR LINQ device implanted at the end of the last treatment, adverse events and severe adverse events will be collected until a week after study visit #9.

**Enrollment and Baseline Study Visits: Study A and Study B**

**Study visit #1: Screening/Enrollment Visit**

Subjects will be consented at the beginning of the screening visit, before any study procedures are performed. This visit will take place at the dialysis unit. If a blood pregnancy test is required, then a sample will be collected at this time and sent to the local lab for processing. Eligibility criteria will be confirmed via review of medical records and medication lists will be reviewed.

**Study Visit #2: Reveal LINQ Insertion/Baseline Visit**

Within 4 weeks of consent, a physical exam will be performed and subjects will have the ILR device implanted at the local site. If coagulation labs are not clinically available within relevant timeframe (72 hours), then these will also be drawn at this visit. Platelet count must be available within 30 days of the procedure or it will be drawn at this visit. Coagulation parameters and platelet count (as needed) may be drawn up to 72 hours prior to the Reveal LINQ visit to ensure that they are available at the time of the procedure. If the subject is not taking an anticoagulant medication, the coagulation parameters and platelet count may be drawn up to 96 hours prior to the procedure. Concomitant medications will be recorded from this visit until one week after the last study related treatment. As needed for scheduling purposes the procedures needed to complete this visit may take place on more than 1 calendar day.

Procedures will be performed in an outpatient or in an office environment. Due to COVID-19 safety precautions, subjects may be provided with a COVID-19 nasal swab test as part of this visit. Conscious sedation (including alprazolam/midazolam/fentanyl) and prophylactic oral or intravenous antibiotics may be used

at discretion of study cardiologist. Subjects will be given a transmitter/charger and a Patient Care Assistant which they will be required to keep for the duration of their participation in the study. ILR tracings will be uploaded automatically whenever patients are within 6.5 feet of the transmitter during the programmed daily transmission time and reviewed at least once every two weeks via a website on a secure platform by the study team for the occurrence of CSA. The subject may be asked to manually upload data from the transmitter throughout the study if they have a higher number of cardiac related events, are enrolled in the substudy, or at the discretion of the PI. This will take a few minutes and the study team will ensure the patient is aware and capable of completing this task. The Baseline Observation Period begins at this visit and continues for 30 days until Study Visit #4.

**Study Visit #3: Week 1 Reveal Visit (+/- 3 days)**

Wound check visit at dialysis unit or the local site. Standard of care labs will be reviewed from participants' medical records. If a particular lab is not available from the clinical records, it is not required to draw it for study purposes at this visit. The assays that will be measured include:

**Chemistry:**

Sodium	Iron
Glucose	Iron Binding Capacity (TIBC)
Urea Nitrogen (BUN)	Ferritin
Serum Creatinine	Albumin
Potassium	Parathyroid Hormone
Chloride	
Calcium	
Phosphate	Single Pool Kt/V (actual)
Bicarbonate	

